- f) Clinical laboratory tests: (Chemistry) alkaline phosphatase, creatinine, ferritin, C-reactive protein, albumin, alanine aminotransferase, amylase, aspartate aminotransferase, gamma glutamyl transpeptidase, total bilirubin, blood urea nitrogen, glucose, lipase, sodium, potassium, calcium; (Hematology) hemoglobin, hematocrit, red blood cell count, white blood cell count and differential (neutrophils, lymphocytes, monocytes, eosinophils, basophils), platelet count. Only in women who are not WOCBP (to confirm postmenopausal status): follicle stimulating hormone at Visit 0.
- g) Viral screening for human immunodeficiency virus (HIV) 1 or 2, hepatitis B, hepatitis C.
- h) Flexibility for visit days: Visit 3 Day 8±1 d; Visit 4 Day 22±2 d; Visit 5 Day 29±3 d; Visit 6 Day 43±4 d; Visit 7 Day 50±4 d; Visit 8 Day 85±7 d; Visit 9 Day 184±9 d.
- i) Only for the first 6 subjects per group. Questioning on and documentation of AEs as well as systemic and local reactions, the latter in case of upcoming dose decision meetings.
- j) Only IMP-related AEs and any SAEs except proven COVID-19 cases which have to be reported regardless on severity and relatedness to the trial drug until the last scheduled FU Visit as described in Section 10.3.1.9.
- k) Blood draw for anti-SARS-CoV-2 antibodies.
- I) For Cohorts 1 and 8, immunization with at least 1 h intervals between subjects for the first 6 subjects and then with of at least 30 min intervals for the remaining 6 subjects. For all other cohorts and for all boost immunization, the intervals between subjects will be at least 30 min.
- m) Oral swipe for SARS-CoV-2 testing either on Day -1 or at the Visit 1 on Day 1.
- n) The timing of the listed "research" blood draw days may be adapted within the 200 mL maximum volume if justified by the collected data. Leftover blood after completion of the immunogenicity assessments may be used for additional analyses as described in Section 8.7 (Genetics) and/or Section 8.8 (Biomarkers).
- For subjects who have given consent, one aliquot of the blood sample drawn for analysis of CMI may be used for HLA typing to allow additional analysis of T-cell receptor repertoire and/or phenotypic characterization of T cells specific to vaccine-encoded antigens.
- p) If HLA typing using the blood sample collected with Lithium Heparin is not conclusive, EDTA-blood will be drawn for HLA testing.
- q) Only cohorts starting prime dosing after approval of protocol amendment 06.

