- k) For Cohort 1, immunization with at least 1 h intervals between subjects for the first 6 subjects and then with at least 30 min intervals for the remaining 6 subjects. For all other cohorts, immunization with 30 min intervals between subjects.
- The listed blood draw days may be adapted if justified by the collected data. Leftover blood after completion of the immunogenicity assessments may be used for additional analyses as descr bed in Section 8.7 (Genetics) and/or Section 8.8 (Biomarkers).
- m) For subjects who have given consent, one aliquot of the blood sample drawn for analysis of CMI may be used for human leukocyte antigen typing to allow additional analysis of T-cell receptor repertoire and/or phenotypic characterization of T cells specific to vaccine-encoded antigens.
- n) Only IMP-related AEs and any SAEs except proven COVID-19 cases which have to be reported regardless on severity and relatedness to the trial drug until the last scheduled FU Visit as described in Section 10.3.1.9.
- o) Only for the first 6 subjects per group. Questioning on and documentation of AEs as well as systemic and local reactions, the latter in case of upcoming dose decision meetings.
- p) If HLA typing using the blood sample collected with Lithium Heparin is not conclusive, EDTA-blood will be drawn for HLA testing.
- q) When entering the follow-up phase, i.e., after completing the EoT Visit, subjects are allowed to participate in other clinical trials not investigating COVID-19 vaccines or treatments.

BioNTech SE	Clinical Trial Protocol	Page 26 of 113
	including Amendments Nos. 01 to 09	Version: 13.0
Confidential	BNT162-01	Date: 12 JAN 2022

r) Record any medications that trial subjects receive during the trial in the CRF starting after Visit 0 and until the respective EoT Visit; record any vaccination, including SARS-CoV-2 vaccination, that subjects receive after the EoT Visit until the last FU Visit in the CRF.

AE = adverse event; CMI = cell-mediated immune testing; CRF = case report form; d = day; ECG = electrocardiogram; EDTA = ethylenediamine tetraacetic acid; EoT = end of treatment (Visit); FU = follow-up (visit); h = hour(s); HLA = human leukocyte antigen; IMP = investigational medicinal product; min = minute(s); SAE = serious adverse event; SARS-CoV-2 = the virus leading to COVID-19; WOCBP = women of childbearing potential.

BioNTech SE Confidential	Clinical Trial Protocol	Page 27 of 113		
	including Amendments Nos. 01 to 09	Version: 13.0		

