- f) Clinical laboratory tests: (Chemistry) alkaline phosphatase, creatinine, ferritin, C-reactive protein, albumin, alanine aminotransferase, amylase, aspartate aminotransferase, gamma glutamyl transpeptidase, total bilirubin, blood urea nitrogen, glucose, lipase, sodium, potassium, calcium; (Hematology) hemoglobin, hematocrit, red blood cell count, white blood cell count and differential (neutrophils, lymphocytes, monocytes, eosinophils, basophils), platelet count. Only in women who are not WOCBP (to confirm postmenopausal status): follicle stimulating hormone at Visit 0.
- g) Viral screening for human immunodeficiency virus (HIV) 1 or 2, hepatitis B, hepatitis C.
- h) Flexibility for visit days: Visit 3 Day 8±1 d; Visit 4 Day 22±2 d; Visit 5 Day 29±3 d; Visit 5a Day 36±3 d; Visit 6 Day 43±4 d; Visit 7 Day 50±4 d; Visit 8 Day 85±7 d; Visit 9 Day 184±9 d; Visit 10 Day 365±14 d; Visit 11 Day 547±14 d; Visit 12 Day 730±14 d.
- i) Only for HIV-positive subjects (done locally).
- j) Visits 8 and 9, only IMP-related AEs and any SAEs. Visits 10, 11, and 12, only any SAEs except proven COVID-19 cases which have to be reported regardless on severity and relatedness to the trial drug until the last scheduled FU Visit as described in Section 10.3.1.9. For subjects who receive non-trial SARS-CoV-2 vaccinations, the AEs expected to be captured after these vaccinations are within the frame of post-marketing safety data reporting (see Section 8.3.1).
- k) Blood draw for anti-SARS-CoV-2 antibodies.
- I) For first immunization in Cohort 13, immunization with at least 30 min intervals between the primary immunizations and 30 min between the boost immunizations. For Cohorts 11 and 12, the interval between the trial subjects will be at least 15 min for the prime immunizations and at least 5 min for the boost immunizations.
- m) Oral swipe for SARS-CoV-2 testing either on Day -1 or at the Visit 1 on Day 1.
- n) The timing of the listed "research" blood draw days may be adapted (within the 200 mL maximum volume) if justified by the collected data. Leftover blood after completion of the immunogenicity assessments may be used for additional analyses as described in Section 8.7 (Genetics) and/or Section 8.8 (Biomarkers). For subjects who receive non-trial SARS-CoV-2 vaccinations, there will be no blood sampling for immunogenicity or cell-mediated immune testing in the FU Visits.

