# 8.3.1 Time period and frequency for collecting AE and SAE information

For Cohorts 1 to 10, all AEs and SAEs will be collected from the date of subject consent until discharge from the trial only IMP-related AEs and any SAEs will be collected.

For Cohorts 11 to 13 and 14, all AEs and SAEs will be collected from the date of subject consent until Visit 7 (the EoT Visit). From Visit 7 through 9 only IMP-related AEs, SAEs, and SARS-CoV-2 infections will be collected. After Visit 9 (e.g., Visits 10, 11, and 12) until the last scheduled FU Visit (i.e., when the subject is discharged from the trial), any SARS-CoV-2 infections and SAEs will be collected.

For subjects in Cohorts 11 to 13 who receive a non-trial SARS-CoV-2 vaccination, AEs/SAEs will be collected as specified above until the date when the subject was vaccinated with the non-trial SARS-CoV-2 vaccine. The AEs expected to be captured after non-trial SARS-CoV-2 vaccination are within the frame of post-marketing safety data reporting.

All SAEs (initial and follow-up reports) will be recorded and reported to the sponsor or designee within 24 h after becoming aware of the event, as indicated in Section 10.3.1.10.

Investigators are not obligated to actively seek AEs or SAEs after conclusion of the trial participation. However, if the investigator learns of any SAE, including a death, at any time after a trial subject has been discharged from the trial, and he/she considers the event to be reasonably related to the IMP administration or trial participation, the investigator must promptly notify the sponsor.

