# 10.3.1.7 Recording and follow-up of AE and/or SAE

## AE and SAE recording

The investigator needs to assess and document any AE regardless of association with the use of the trial treatment during the period of observation (starting from Visit 0 until 21 d after the last immunization or trial subject discharge from the trial, whichever one is later). To ensure trial subject safety during the trial, safety will be monitored from Visit 0 (screening) until at least (approximately) 6 months after the last immunization.

BioNTech SE
Confidential

- Data pertaining to AEs will be collected during each trial visit either based on the trial subject's spontaneous description or investigator's inquiry or discovered in the course of examinations done during the visit, clinical significance of any sign or symptom needs to be evaluated by the investigator.
- Clinically significant findings need to be documented as AEs in the source data and CRF. Findings that are evaluated and documented in the source data as not clinically significant (e.g., an abnormal laboratory value without any clinical manifestation), should not be documented as AE.
- The investigator will then record all relevant AE information in the CRF and perform an assessment on:
  - Intensity, see the section "Assessment of intensity" in Section 10.3.1.11 for guidance on the assessment of intensity
  - Seriousness
  - Outcome
  - Causal relationship of the AE to the trial treatment
  - Any trial treatment action and/or any other action taken
- All assessments as well as AE term (diagnosis/description), start date and time of onset, end date and time need to be documented in the CRF.
- There may be instances when copies of medical records for certain cases are requested by the sponsor. In this case, all trial subject identifiers, with the exception of the trial subject number, will be redacted on the copies of the medical records before submission to the sponsor.
- To avoid colloquial expressions, the AE should be reported in standard medical terminology. The investigator will attempt to establish a diagnosis of the event based on signs, symptoms, and/or other clinical information. Whenever possible, the diagnosis (not the individual signs/symptoms) will be documented as the AE. If a definitive diagnosis is not possible, the individual signs and symptoms should be recorded.

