#### 6.4.3. Adverse Events

#### Definition

For detailed information on adverse events see section 10.3 of the protocol.

Adverse events (AEs) will be coded using the Updated Version MedDRA® 23.0 including specific terms for COVID-19 to get a system organ class (SOC) and preferred term (PT) for each AE.

A treatment emergent adverse event (TEAE) is defined as any AE with an onset after the first immunization (if the AE was absent before the first immunization) or worsened after the first immunization (if the AE was present before the first immunization). AEs with an onset date more than 28 days after the last immunization will be considered as treatment emergent only if assessed as related to IMP by the investigator. AEs that cannot be determined to not be treatment emergent due to missing date or time will be defined as TEAE.

Clarification: To clarify the definition in the protocol, AEs with an onset date at the date of the first immunization will only be considered as treatment emergent if the AE occurred after the first immunization.

The TEAEs will be evaluated for the following time intervals, clarifying and harmonizing the intervals defined in the protocol:

- Prime immunization up to boost immunization or day 28 (inclusive) after initial immunization (whatever comes first)
- Boost immunization up to day 28 (inclusive) after boost immunization
- All TEAEs (regardless of relationship assessment) occurring from

- Prime immunization up to day 28 after boost immunization (inclusive).
- If no boost immunization, up to 28 days (inclusive) after prime immunization
- All TEAEs assessed as related through visit 10.

The intervals starting or ending with an immunization, will start or end with the date and time of the immunization. TEAEs are assigned to the time intervals according to their start date and time. AEs with missing date will be assigned to each of the respective intervals if it cannot be ruled out, that it belongs to the time interval.

Deviating from the protocol, the time intervals including 7 days after each immunization will not be analyzed.

AEs will be evaluated for the following time interval 'After Day 28 after boost or after prime (if no boost)':

All AEs (regardless of relationship assessment) occurring

- After day 28 after boost immunization
- o If no boost immunization, after 28 days after prime immunization

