#### AEs

The number and percentage of subjects reporting at least one AE and the number of AEs will be summarized for the above defined time interval 'After Day 28 after boost or after prime (if no boost)' and the following AE types:

- Any AE
- Related AE
- Grade >=3 AE

- Related grade >=3 AE
- AEs with dose limiting toxicity (DLT)
- Any serious adverse event (SAE)
- Related SAE
- Deaths
- Any AEs linked to confirmed COVID-19 cases (defined as AEDECOD = 'COVID-19')

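### The SAP's 'After Day 28' table has all-causality AE rows for a period in which unrelated non-serious AEs are mostly not collected, so the rows are understated and boosted and unboosted cohorts are not comparable

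*SAP*

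**What the plan says.** **The table.** SAP 6.4.3 (Definition) sets up an interval that opens after day 28 after boost, or after day 28 after prime if no boost was given. It takes in "All AEs (regardless of relationship assessment) occurring" in that period. Under the sub-heading AEs, subject counts and percentages "will be summarized for the above defined time interval 'After Day 28 after boost or after prime (if no boost)' and the following AE types". The types include 'Any AE' and 'Grade >=3 AE', beside related, DLT, SAE, death and COVID-19 rows. Neither place has a caveat, a closing date or a person-time column. Under SAP 6.1.1, cohorts are columns of one table per vaccine type, with a cohort-total.

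**What is collected after the EoT Visit.**
- Protocol Table 6, footnote j (prime/boost, Cohorts 1 to 10): "Only IMP-related AEs and any SAEs except proven COVID-19 cases which have to be reported regardless on severity and relatedness to the trial drug". The wording is awkward, but the effect is that related AEs, SAEs and every proven COVID-19 case are recorded.
- Table 7, footnote n (BNT162c2 single dose) applies the same rule: "Only IMP-related AEs and any SAEs except proven COVID-19 cases".
- Table 8, footnote j (Cohorts 11 to 13) narrows it with time: "Visits 8 and 9, only IMP-related AEs and any SAEs. Visits 10, 11, and 12, only any SAEs except proven COVID-19 cases", with the same COVID-19 provision.
- Table 9, footnote i (Cohort 14): related AEs, SAEs and proven COVID-19 at Visit 9.
- Protocol 8.3.1 agrees for Cohorts 11 to 14. Its sentence for Cohorts 1 to 10 has lost some words. It begins with all AEs and SAEs from consent and ends "until discharge from the trial only IMP-related AEs and any SAEs will be collected", without naming the visit at which the rule changes.

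**Text that points the other way.** Protocol 10.3.1.7: "The investigator needs to assess and document any AE regardless of association with the use of the trial treatment during the period of observation". That period runs to discharge from the trial if this is later than 21 d after the last immunization.

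**The concern.** A row labelled 'Any AE' promises every adverse event in the period. If unrelated non-serious events are not recorded for most or all of that period, the row mainly counts events judged related, serious or COVID-19. A reader of the report could take a low late-AE percentage as reassurance when it reflects the collection rule.

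The length of full collection inside the interval also depends on whether the boost was given. Boosted and unboosted cohorts stand side by side in one vaccine's table. The unboosted column has weeks in which an unrelated event could be recorded and the boosted column has almost none, so a difference between them could be produced by the schedule alone.

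**Working it through.** **Inputs.** Boost Day 22±2. EoT is Visit 7, Day 50±4, for prime/boost and Visit 6, Day 43±4, for single dose. Nominal last visit is Day 184, or Day 730 for Cohorts 11 to 13. Sources: Protocol 1.3, Tables 6 to 9, and Protocol 4.4.

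**Step 1: reproduce the plan's own figure.** The primary endpoint in Protocol section 3 equates 28 d after boost with trial day 50. Boost on Day 22 gives 50 − 22 = 28. The later days-since-dose entries also agree: 85 − 22 = 63, 184 − 22 = 162, 730 − 22 = 708.

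**Step 2: full AE collection inside the interval.** Days of full collection = (days from last dose to EoT) − 28. Nominal interval length = (days from last dose to last visit) − 28.

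| Group | Full collection | Interval length | Share |
|---|---|---|---|
| Boosted, Cohorts 1–10 and 14 | 28 − 28 = 0 d | 162 − 28 = 134 d | 0% |
| Boosted, Cohorts 11–13 | 28 − 28 = 0 d | 708 − 28 = 680 d | 0% |
| BNT162c2 single dose | 42 − 28 = 14 d | 183 − 28 = 155 d | 9.0% |
| Prime/boost, no boost given, last visit Day 184 | 49 − 28 = 21 d | 183 − 28 = 155 d | 13.5% |

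Visit windows place EoT between 46 − 24 = 22 and 54 − 20 = 34 d after boost. A boosted subject therefore has at most 34 − 28 = 6 d of full collection in the interval.

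**Step 3: related events in Cohorts 11 to 13.** From Visit 9 to Visit 12 is 708 − 162 = 546 of the 680 d. In that stretch only SAEs and COVID-19 cases are recorded, so non-serious related AEs are missing from 'Related AE' and 'Related grade >=3 AE'. SAP 6.4.3 also lists an interval for related TEAEs through Visit 10, which asks for non-serious related events that are not collected after Visit 9.

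**Step 4: where the contrast falls within one table.** In BNT162a1, six subjects of the starting cohort received no Day 22 dose (Protocol Table 1, footnote b). In BNT162b1, the 60 µg boost was not administered (note to Protocol Table 2). Subjects without a boost still complete the schedule (note to Protocol Table 6). These columns have about 21 d of full collection beside boosted columns with about 0 d. In the BNT162b2 table, cohorts nominally followed to Day 184 stand beside, and are totalled with, Cohorts 11 to 13, nominally followed to Day 730.

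**Step 5: illustration.** The documents give no rate for unrelated, non-serious, non-COVID AEs. Assume 0.5, 1 or 2 per subject-year at a constant rate, with P(at least one) = 1 − exp(−rate × days / 365.25). Percent of subjects with such an event, recorded against occurring:

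| Group | 0.5 per year | 1 per year | 2 per year |
|---|---|---|---|
| Boosted, to Day 184 | 0 vs 17% | 0 vs 31% | 0 vs 52% |
| Boosted, Cohorts 11–13, to Day 730 | 0 vs 61% | 0 vs 84% | 0 vs 98% |
| BNT162c2 single dose | 1.9 vs 19% | 3.8 vs 35% | 7.4 vs 57% |
| Unboosted prime/boost | 2.8 vs 19% | 5.6 vs 35% | 10.9 vs 57% |

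At 1 per year the unboosted column would show 5.6% and the boosted column 0%, although the true proportions are 35% and 31%.

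**The case against.** The best defence is that this is one supplementary descriptive table in a trial with no hypothesis under test, and that its SAE, death and COVID-19 rows are collected throughout. That is right and limits the consequence, but it does not make the two all-causality labels accurate.

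A second defence is 10.3.1.7: if any AE is documented until discharge, nothing is understated. Taken alone it would have that effect. But it conflicts with the footnotes of all four schedules and with 8.3.1 for Cohorts 11 to 14, and 10.3.1.10 itself sends the reader to 8.3.1 for the period of observation. Sites following different passages would collect differently, which would not make the rows interpretable.

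Some stronger readings are tempting and are not supported:
- *Single-dose and prime/boost groups would show artefactual differences.* Their full-collection periods do differ, but SAP 6.1.1 puts these regimens in separate tables. The side-by-side problem is boosted against unboosted cohorts of one vaccine.
- *The related share of late AEs is inflated.* No such statistic is planned; percentages use the number of subjects in the analysis set.
- *Only related AEs and SAEs survive after EoT.* Proven COVID-19 cases are recorded whatever their severity or relatedness and are not understated.
- *Section 8.3.1 sets two rival rules for Cohorts 1 to 10.* The sentence is incomplete, and the footnotes to Tables 6 and 7 supply the cut-off.
- *The two rows should simply be deleted.* Single-dose and unboosted subjects have 14 and 21 d of genuinely full collection after day 28. Unrelated events with onset there are not TEAEs by definition, so this table is their only summary outside the listings.

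**Conclusion.** The mismatch holds. Under the schedules, 'Any AE' and 'Grade >=3 AE' after day 28 omit unrelated, non-serious, non-COVID events for nominally all of the interval in boosted subjects (0 d of full collection, at most about 6 d), for all but about 14 d in BNT162c2 single-dose subjects and for all but about 21 d in unboosted prime/boost subjects. The rows are understated, and they are not comparable between boosted and unboosted cohorts within a vaccine's table. For Cohorts 11 to 13 the related-AE rows are also incomplete after Visit 9.

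This assumes that sites follow the schedule footnotes rather than 10.3.1.7, and it uses nominal visit days. The 680 d is an upper nominal figure, because subjects in Cohorts 11 to 13 who receive a non-trial SARS-CoV-2 vaccination are discontinued (Protocol 7.2) and data assessed after a non-trial vaccination are excluded (SAP 6.1). The percentages in the illustration rest on assumed rates. The structural gap does not.

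A reader might infer that the primary safety result is compromised. The documents do not support that: the primary unsolicited-TEAE endpoint covers the period up to day 28 after the last dose, and this table starts after it. The point is worth correcting but confined to a descriptive late-safety table.

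**What to change.** In SAP 6.4.3:
- End 'Any AE' and 'Grade >=3 AE' at the EoT Visit. Alternatively, relabel them as collected AEs (related, serious or COVID-19) and count only those kinds. If relabelled, state that in Cohorts 11 to 13 non-serious related events stop at Visit 9.
- End 'Related AE' and 'Related grade >=3 AE' at Visit 9.
- Keep SAE, related SAE, death and COVID-19 rows for the full interval.
- Footnote the collection rule and show follow-up time per cohort. Interval lengths still differ (134, 155 and 680 d nominally) and, if the all-causality rows end at EoT, the boosted columns will be nearly empty by design.
- Check the related-TEAE interval through Visit 10 against the Visit 9 cut-off.

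In the protocol, complete the 8.3.1 sentence for Cohorts 1 to 10 and reconcile 8.3.1 and 10.3.1.7 with the schedule footnotes, so that one collection rule is stated.

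The cost is a few row definitions, one footnote, one follow-up-time line per cohort and a wording correction. No new data are needed.
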